4.1.4. Blinding and Randomization

The first ten eligible subjects will be randomized in a 1:1 ratio according to a pre-determined block randomization procedure to receive either FMT or placebo. If safety allows, the remaining cohort of 50 eligible subjects will be randomized in a 1:1 ratio according to a pre-determined block randomization procedure to receive either FMT or placebo. An unblinded pharmacist or delegate will maintain the randomization list ensuring subjects are randomized appropriately and dispensed the correct treatment. The investigator, research personnel and study subjects will be blinded to treatment assignments.

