0.5-1	2	3 times a day				
1-1.5	3	3 times a day				
1.5-2	4	3 times a day				

*BSA will be calculated as **BSA = SQRT [(cm*kg)/3600]**

2) A third antibiotic metronidazole administered orally (PO) as a separate capsule according to the following weight-based dosing parameters:

Patient Wt (kg)	Dose (mg)	Frequency			
12.5 - 25.0	125	2 times a day			
25.0 - 37.5	250	2 times a day			
37.5 - 50.0	375	2 times a day			
>50.0	500	2 times a day			

Corresponding placebo for each antibiotic will be supplied and distributed by the BCH Research Pharmacy.

Clinical data including symptom logs, medications and disease activity and stool samples will be collected at the time of study entry and after completion of the antibiotic regimen. Routine laboratory analysis will be done at the time of enrollment and before commencing study treatment.

Subjects who meet all eligibility criteria will be randomized to receive either FMT or placebo.

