7. STATISTICAL CONSIDERATIONS

7.1. Power Calculation

The primary aim of this phase I/II study is to establish whether or not FMT is a safe treatment for children and young adults with UC. Based on clinical experience, adverse events (AEs) in IBD patients are common and include abdominal pain, cramping, diarrhea, fever, bloody stool, vomiting, frequent defecation, joint pain, and eye pain. It's estimated that 70% of patients in any given year will experience a flare of their disease and have some or a combination of these symptoms. Safety, therefore, needs to be assessed relative to the high prevalence of AEs in this population. For the primary outcome, we will take any new reported SAEs or worsening of the existing AEs during the study period following enrollment into account.

The study will be powered for equivalence in the proportion of new SAEs or worsening of the existing AEs, assuming null (Ho) and alternative (Ha) hypotheses defined as follows:

$$\begin{split} & \text{Ho: } p1-p2 \leq \text{-}\delta_L \ \text{ or } p1-p2 \geq \delta_U. \\ & \text{Ha: } \delta_L \leq p1-p2 \leq \delta_U \end{split}$$

where p1 is the proportion of new SAEs or worsening of the existing AEs in the placebo group, p2 is the proportion in the FMT group, δ_L is the lower margin and δ_U is the upper margin. We expect to enroll a total of 60 patients into this study for a total of 30 FMT and 30 placebo patients. Assuming the rate of new incident SAEs or worsening of existing AEs in the placebo group is 10%, there will be 82% power to reject Ho that the difference in proportions is 0.20 or greater from zero in the same direction. Similarly, we will have an 85% power to reject a difference of 0.25 or greater if the rate of new incident SAEs or worsening of existing AEs increases to 15%.

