7.3. Data Analysis

All patients who are eligible, randomized, and have received at least one-dose of the study medication including antibiotics/placebo in the first week will be included into the analysis for primary outcomes to assess the safety and tolerability of FMT, as this will be a per protocol (and not intent-to-treat) analysis . Continuous variables will be presented as mean and standard deviation (SD) or median and interquartile range (IQR), depending on the distribution of the data. Categorical variables will be presented as number and percentage. Disease severity (PUCAI) and patient characteristics at baseline will be compared between the treatment groups to determine whether or not randomization resulted in balanced groups. Methods of 2-group comparison will include Student's t-test, the Mann-Whitney test, Pearson chi-square test, and Fisher exact test, depending on the distribution of the variable under consideration. The primary outcome of safety will be assessed via a 2×2 cross-tabulation, where the proportion of patients with new incident SAEs or upgrade of existing AEs in the FMT group will be compared to the proportion in the placebo group. Two one-sided tests for equivalence (32) will be constructed and the overall *P* value taken to be the larger of the lower and upper tests. Statistical significance will be assessed at *P*<0.05.

For the second outcome, we will use longitudinal data analysis methods to investigate changes in inflammatory biomarkers including stool calprotectin, stool lactoferrin, serum ESR/CRP, albumin, and hematocrit over the study period. Generalized Estimating Equations will be performed to examine the association between FMT and changes in these biomarkers.

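### The biomarker GEE has no stated baseline, and one value it could use (Day 0) already follows antibiotics in the FMT arm only

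*Combined protocol and SAP*

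**What the plan says.** Section 7.3 assigns the inflammatory markers (stool calprotectin, stool lactoferrin, ESR/CRP, albumin, hematocrit) to longitudinal methods covering the whole study: "Generalized Estimating Equations will be performed to examine the association between FMT and changes in these biomarkers". It names no reference time point, baseline covariate, cohort term or working correlation. Baseline data are otherwise used only to compare the arms for balance.

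Section 5.2.1 provides two measurements before FMT: "stool samples will be collected at the time of study entry and after completion of the antibiotic regimen". It places routine laboratory tests at enrollment and again just before study treatment. The schedule in section 5.1 puts stool at Day -8 and Day 0, and blood in the screening window (Day -90 to -9) and at Day 0. Antibiotics, or placebo antibiotics in the placebo arm, start after randomisation and finish before Day 0. Section 5.2.3 confirms that the placebo arm has had no antibiotics by the end of the blinded period.

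Randomisation is run in two parts. The first ten subjects, who have narrower eligibility (age 12 or over, PUCAI below 65), are randomised 1:1, and then "the remaining cohort of 50 eligible subjects will be randomized in a 1:1 ratio" (section 4.1.4).

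**The concern.** An analysis of change needs a starting value, and the two candidates are not equivalent. The earlier one precedes all randomised treatment. The later one, Day 0, comes after part of the randomised package in one arm and after placebo in the other. Section 1.2 gives the plan's own reason to expect antibiotics to matter: it cites a retrospective pediatric cohort in which 7 of 15 patients reached complete remission on antibiotics. Two analysts following section 7.3 could therefore choose different baselines and report different arm effects from the same data.

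Two further matters depend on the same missing specification. If the response is a raw change score, precision is lost compared with adjusting for the same baseline. If all visits to the end of the study enter the model, blinded and open-label data are mixed.

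**Working it through.** **Inputs.** The plan states no SD, correlation, effect size or power for any biomarker, so there is no biomarker figure to reproduce. The usable planning input is the sample size: "We expect to enroll a total of 60 patients into this study for a total of 30 FMT and 30 placebo patients". Values of a and ρ below are assumptions.

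**Step 1. What each candidate baseline follows.**

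| | Last pre-antibiotic value | Treatment in between | Day 0 value |
|---|---|---|---|
| FMT arm | Screening blood, Day -8 stool | Active antibiotics | Post-antibiotic |
| Placebo arm | Screening blood, Day -8 stool | Placebo antibiotics | Untreated |

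**Step 2. Effect of using Day 0.** Let θ be the Week 8 arm difference produced by everything randomised (antibiotics plus FMT). Let a be the antibiotic shift in the Day 0 mean of the FMT arm, and ρ the within-arm correlation of Day 0 with Week 8, with equal SDs.

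- Change from Day 0 estimates θ − a.
- Adjustment for Day 0 (slope ρ) estimates θ − ρa.
- Change from, or adjustment for, a pre-antibiotic value estimates θ.

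| a (SD) | Removed by change from Day 0 | Removed by Day 0 as covariate, ρ = 0.3 / 0.5 / 0.7 |
|---|---|---|
| 0.25 | 0.25 | 0.075 / 0.125 / 0.175 |
| 0.50 | 0.50 | 0.15 / 0.25 / 0.35 |

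**Step 3. Precision for a given baseline, one follow-up value.** In units of the marker variance, the change score has 2(1 − ρ) and the baseline-adjusted analysis has 1 − ρ². The ratio is (1 + ρ)/2. The total N at which a change-score analysis matches 60 adjusted patients is 60 × 2/(1 + ρ). Power is for 30 per arm at 0.72 SD, the difference that a follow-up-only comparison detects with 80% power.

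| ρ | Change | Adjusted | Ratio | Matching N | Power, change | Power, adjusted |
|---|---|---|---|---|---|---|
| 0.3 | 1.40 | 0.91 | 0.65 | 92 | 66% | 84% |
| 0.5 | 1.00 | 0.75 | 0.75 | 80 | 80% | 90% |
| 0.7 | 0.60 | 0.51 | 0.85 | 71 | 95% | 98% |

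This compares two uses of the *same* baseline. An older pre-antibiotic value may correlate less with Week 8 than Day 0 does. For example, adjustment at ρ = 0.3 (0.91) is less precise than change from a Day 0 value at ρ = 0.7 (0.60). The reason to reject Day 0 is therefore Step 2, not precision.

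**Step 4. Visits after Week 8.** Under section 5.2.3, treatment is unblinded after the Week 8 dose. Open-label FMT is offered to placebo subjects who did not improve and to FMT subjects who did; the others go to follow-up. Treatment after Week 8 thus depends on both arm and response, and later visits no longer give a randomised comparison of FMT with placebo.

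**Step 5. The two cohorts.** For a continuous marker whose mean differs by D SD between the first 10 and later 50, the share of variance explained is b/(1 + b), with b = (10/60)(50/60)D². It is 0.9%, 3.4% or 12.2% for D = 0.25, 0.5 or 1.0.

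For the primary 2×2, first reproduce the plan's figure, "there will be 82% power to reject Ho that the difference in proportions is 0.20 or greater from zero in the same direction". With a 10% rate and one one-sided test at 0.05, Φ(0.20/√(2 × 0.10 × 0.90/30) − 1.645) = 82.6%. (The two-test equivalence procedure in section 7.3 would give 65.1%; that is a separate matter.)

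The variance share removed by stratifying is (1/6)(5/6)d²/(p(1 − p)), where d is the difference in event rate between cohorts. It is 1.2% for rates of 5% and 15%, and 3.3% for 5% and 25%. Holding the overall rate at 10%, rates of 5% and 11% give 0.6%; rates of 20% and 8% give 2.2% and move the 82.6% to 83.3%. Only an extreme split (30% and 6%) reaches 8.9%.

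**The case against.** The strongest reply is that section 7.3 is silent rather than wrong. It never names Day 0 as baseline, and longitudinal methods could mean a repeated-measures model with every visit as a response. That is fair, and it makes the losses in Steps 2 and 3 conditional. It does not remove the point. Such a model still needs a reference visit before it can report change, and with complete data and free arm-by-visit means its arm difference in change equals the change-score difference.

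It can also be argued that starting from Day 0 isolates FMT from the antibiotics. The design cannot support that: the placebo arm has no antibiotics, and subtracting the Day 0 shift would isolate FMT only if the shift lasted unchanged to Week 8.

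Some practical objections stand. Screening blood may be about 90 days old at Day 0. Section 5.1 does not treat a missing stool sample as a deviation, so Day -8 values may be absent. The markers are secondary outcomes with no stated power.

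A reader might also infer more than the documents support:

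- *The analyses ignore pre-treatment status.* A change uses an earlier value, and the primary outcome counts new SAEs or worsening of existing AEs.
- *The markers are analysed untransformed.* The plan does not say either way.
- *All needed values are already collected.* Lactoferrin appears in section 7.3, but the stool-biomarker footnote in section 5.1 lists only calprotectin.
- *Pooling the cohorts confounds the comparison.* Both are randomised 1:1, so it does not.

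**Conclusion.** The point holds as a gap in the secondary biomarker analysis that should be closed before unblinding. The reference time point is undefined, and one of the two candidates is altered by randomised treatment in one arm only. If Day 0 is used, the arm difference loses all of the antibiotic shift as a change score, or about ρ times it as a covariate. The documents give no value for that shift.

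If a change score is used, baseline adjustment would have 65% to 85% of its variance for assumed correlations of 0.3 to 0.7. That range assumes one follow-up value, equal SDs and the same baseline in both analyses. Including visits after Week 8 would add data that are not a randomised comparison of FMT with placebo.

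The primary safety comparison is not called into question here. Stratifying it by cohort would gain only about 1–3% of variance and has no confounding to remove.

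**What to change.** In section 7.3:

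1. Define baseline as the last value before the first antibiotic or placebo-antibiotic dose: screening labs for blood and the Day -8 sample for stool. State that Day 0 is not a baseline.
2. Model each marker at the blinded post-treatment visits on arm, visit, arm-by-visit and baseline, with an indicator for the first 10 versus the later 50. Name Week 8 as the main contrast. Report data after Week 8 descriptively.
3. Give a rule for missing baselines. One option is to enter baseline as a response with a common mean across arms. The working correlation must then not be independence, because the baseline would do no adjusting.
4. Reconcile lactoferrin between section 7.3 and the schedule.

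Optional: log transformation, a small-sample corrected standard error for about 60 clusters, and cohort stratification of the primary 2×2. In the primary, the first-10 stratum would expect only 1 to 1.5 events at the planned 10–15% rates, so stratifying adds some fragility.

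Items 1 to 3 cost SAP wording only, with no new visits or patients. The price is an older blood baseline and some missing stool baselines, which may reduce the precision gained from adjustment.

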8. DATA CAPTURE AND RECORD KEEPING

All study data will be captured in a 21CFR Part 11 compliant INFORMTM database. Data and source documents will be maintained in compliance with ICH-GCP and local and national regulatory requirements.

By conducting this study, the investigator affirms that all study results and information furnished will be maintained in strict confidence. Such information will be communicated to the investigator's review committee under an appropriate understanding of confidentiality. A published summary of the results of this study is not inconsistent with the preceding affirmation of confidentiality.

All subjects will be actively followed by an investigator at Boston Children's Hospital within the Division of Gastroenterology & Nutrition/ Inflammatory Bowel Disease Center for the duration of the study. The patients will undergo routine visits with clinical staff as is described and a running log of symptoms, medication(s)/medication change(s), and adverse events will be maintained. This information will be collected by case report forms for entry in the INFORMTM database and will be signed-off by the Principal Investigator. The subjects' progress in the study and any changes to their treatment plans will be reviewed with the study team at regularly scheduled weekly study team meetings while the patient remains on the study protocol. Others providing care to the patients will be included to the extent needed to provide appropriate medical care to the patients with patient permission.

9. PROTECTION OF HUMAN STUDY SUBJECTS

9.1. Declaration of Helsinki and Ethical Review

The study will be conducted in accordance with the protocol, applicable ICH Guidelines, Good Clinical Practice and the World Medical Association (WMA) Declaration of Helsinki and its amendments concerning medical research in humans.

In accordance with guidelines and U.S. Code of Federal Regulations applicable to clinical studies, the protocol and informed consent/assent forms will be reviewed and approved by the Boston Children's Hospital Institutional Review Board (IRB). The investigator will inform the IRB and FDA of subsequent protocol amendments and reportable events as defined by IRB policy and FDA regulation.

9.2. Informed Consent

In accordance with applicable guidelines, informed consent/assent will be documented by the use of a written informed consent approved by the IRB and signed by the subject and/or subject's parent or guardian before any screening and protocol specific procedures are performed.

The investigator (or designee) will explain to the subject and/or the subject's parent or guardian the nature of the study, the action of the study treatment, and any risks and benefits. The subject and/or subject's parent or guardian will be informed that participation is voluntary and that the subject can be withdrawn from the study at any time without prejudice to their subsequent care.

The subject and/or the subject's parent or legal guardian will be given a copy of the fully executed consent/assent and the original will be maintained with the subject's records.

9.3. Inclusion of Women, Minorities, and Children (Special Populations)

Eligible male and female subjects who are members of minority groups and their subpopulations will not be excluded from the study. Children 5 years of age or older will be included in the study.

